7.6 CRF: Resource utilization

The study physician will complete a hard copy CRF documenting the patient's medical resource utilization related to GERD such as office visits, prescriptions, hospitalizations etc at month 6 and 12 following study entry. Data regarding over the counter medication and visit to other

physicians will be collected from the patient directly via the patient survey document at month 3, 6, 9 and 12 from study entry.

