7.9 Study Assessments

Data will be collected using a case report form, a patient baseline survey, and four follow-up patient surveys at 3, 6, 9 and 12 months. A summary of each assessment appears in the sections below.

Schedule of Completion	Total Questions	V1	3 months	6 months	9 months	12 months
Physician CRF						
Eligibility and demographics, history, comorbidities	20	X				
Physician CRF / Patient Survey:						
Resource Utilization						
Hospital visits, physician's office visits, prescriptions	~10	X		X		X
Patient Survey:						
Resource Utilization						
Over the counter medication, other physicians			X	X	X	X
Anxiety & Depression						
Hospital Anxiety and Depression Scale (HADS)	14	X				X
Symptom Frequency and Severity						
Reflux Disease Questionnaire (RDQ-RI)	26	X	X	X	X	X
GERDQ	6	X		X		X
Quality of Life						
Quality of Life in Reflux and Dyspepsia (QOLRAD-RI)	25	X		X		X
EQ-5D	6	X		X		X
Short Form 36 (SF-36)	36	X		X		X
Work Productivity						
Work Productivity and Activity Impairment for Patients with Gastroesophageal Reflux Disease (WPAI-GERD)	6	X	X	X	X	X

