8.1 Case Report Forms

Physicians will complete the paper enrolment CRF at the time of the enrollment visit. At month 6 and month 12 the physician will additionally complete a paper CRF for collection of resource utilization data.

Physicians will provide a copy of the CRF and a copy of the informed consent form to i3. The completed CRFs are AZ Property and i3 Innovus will not disclose them to third parties, except for authorized representatives of AZ or appropriate regulatory authorities, without written permission from AZ. AZ will not receive Protected Health Information (PHI) contained in these CRFs.

The study physician will be responsible for completing, reviewing and approving the portion of the case report form relating to the enrollment visit and follow-up contacts.

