10.4 Calculation of Direct Costs: Medical Resource Utilization

Using physician-reported resource utilization data and OTC medications collected from the patients, unit cost for individual services will be derived for the purpose of estimating costs. Following database lock, a unique list of the health care resources reported will be obtained and unit costs for each resource will be identified from standard costing sources. Standard cost sources will include national administrative databases (e.g., hospitalization, ER visit) and patient surveys for outpatient procedures. Unit costs of medications will be obtained from the Vidal. These unit costs will be applied to the resource utilization reported by the patients and used to calculate overall costs of healthcare. Costs will be computed from the third party payer perspective.

The mean cost of healthcare will be reported by visit (at study entry, 6 months and 12 months) and type of healthcare resource use.

The mean cost of healthcare resource use will also be reported by physician type (GP vs specialist), patients' characteristics (age class, gender, BMI class) and frequency and severity of symptoms. The summary statistics will be reported over time and by group in the form of tables and graphs.

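### Section 10.4 reports healthcare cost at study entry beside 6 and 12 months, but the entry value has no defined period, lacks OTC medication, and rests on contradictory collection rules

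*Protocol*

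**What the plan says.** **Planned output.** Section 10.4 reports mean healthcare cost "by visit (at study entry, 6 months and 12 months", and also by type of healthcare resource. It adds: "The summary statistics will be reported over time and by group in the form of tables and graphs".

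**Cost inputs.** The same section opens by naming them: "Using physician-reported resource utilization data and OTC medications collected from the patients".

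**Collection of physician-recorded use.** Section 7.6 has the physician document GERD-related use "such as office visits, prescriptions, hospitalizations etc at month 6 and 12 following study entry". Section 8.1 agrees: "At month 6 and month 12 the physician will additionally complete a paper CRF for collection of resource utilization data". Section 7.9.1 lists hospitalisations, emergency and office visits, referrals, procedures and prescriptions only under the heading for data during the study. Its enrolment list has GERD treatment and history, concurrent conditions and medications, and PPI type, dose and duration. The synopsis also separates a recruitment CRF (history, demographics, comorbidities) from six-monthly record extraction.

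The schedule table in Section 7.9, however, marks hospital visits, office visits and prescriptions at V1 as well as at 6 and 12 months. Section 4 has medical-record data collected at baseline, month 6 and month 12. Section 10.3 plans a retrospective description at entry that includes mean level of resource use by type.

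**Collection of patient-reported use.** The schedule row "Over the counter medication, other physicians" is marked at 3, 6, 9 and 12 months and not at V1. Section 7.6 gives the same months, and Section 7.8 adds these pages only to the follow-up packages.

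**The concern.** A by-visit table and a graph over time invite the reader to look across the columns. That is sound only if each column covers the same length of time and the same items. Here the month 6 and month 12 values naturally cover six months each and include OTC medication. The entry value covers a period that the protocol does not state, and cannot include OTC medication.

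Resource use and cost per patient are primary objectives (Section 3.1). Section 10.6 also plans regression models for costs and longitudinal models of the study endpoints. It does not say whether the entry value enters them. If it does, the same mismatch is carried into estimates of how cost changes with symptoms.

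This goes beyond detail left to an analysis plan. Collection times are fixed in the protocol, and no later document can recover OTC use that was not asked about at V1.

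**Working it through.** The plan states no figure on this point, so there is none to reproduce. The check sets the passages side by side and then illustrates the size.

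**1. Is physician-recorded use collected at entry?**

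| Place | Entry | Months 6 and 12 |
|---|---|---|
| Synopsis, Procedures | history, demographics, comorbidities only | yes |
| 7.6 | not mentioned | yes |
| 7.9.1 | treatment history and PPI details; no visits or hospitalisations | yes |
| 8.1 | enrolment CRF; resource use not mentioned | yes |
| 7.9 schedule | marked at V1 | yes |
| Section 4 | medical-record data at baseline | yes |
| 10.3 | retrospective history, with mean resource use | not addressed there |

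The passages do not agree.

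**2. What period would an entry value cover?** None of these passages gives a look-back. Inclusion criterion 4a requires a GERD history of at least 6 months, so an unbounded history would differ in length between patients.

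**3. Which components would it contain?** OTC medication is a cost input in 10.4 and is collected at months 3, 6, 9 and 12 only. The entry total lacks it even if V1 physician data exist.

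**4. Size, with no true change in the rate of cost.** Let W be the entry look-back in months and s the share of cost from items not collected at entry. Both are assumptions. The follow-up value is taken to cover 6 months.

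- Entry cost / 6-month cost = W × (1 − s) / 6
- Apparent change from entry to month 6 = 6 / [W × (1 − s)] − 1

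| W (months) | s = 0: ratio, change | s = 10%: ratio, change | s = 30%: ratio, change |
|---|---|---|---|
| 1 | 0.17, +500% | 0.15, +567% | 0.12, +757% |
| 3 | 0.50, +100% | 0.45, +122% | 0.35, +186% |
| 6 | 1.00, 0% | 0.90, +11% | 0.70, +43% |
| 12 | 2.00, −50% | 1.80, −44% | 1.40, −29% |

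With W = 6, s = 5% gives 1/0.95 = 1.05 and s = 20% gives 1/0.80 = 1.25. The sign turns at W = 6/(1 − s): 6 months for s = 0, 6/0.9 = 6.7 months for s = 10%, and 6/0.7 = 8.6 months for s = 30%.

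**5. What is not touched.** The 12-month cost per patient sums use from entry to month 12 and does not draw on the entry column.

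**The case against.** Several counter-arguments have force.

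- **Entry data may well exist.** Sections 7.6 and 8.1 are silent on V1 rather than excluding it, and 8.1 describes the later CRFs as additional. The schedule, Section 4 and Section 10.3 all point to some entry data. A reader of 7.6 alone might infer that entry resource use is not collected at all. The documents do not support that; they support a contradiction.
- **No comparison is specified.** Section 10.4 says costs are reported, and the study tests no hypotheses. A reader might infer a planned entry-versus-follow-up contrast, but none is written. What stands is that a by-visit table and a graph over time display the three values together.
- **No direction follows.** A reader might expect an artificial rise, to be read as the cost of becoming a partial responder. With a 12-month look-back the artefact is a fall.
- **Visits to other physicians are doubtful as a mismatch.** The opening of 10.4 names physician-reported use and OTC medication as inputs, so these visits may be left out of cost at every visit. The point rests on OTC medication.
- **Reporting by resource type partly exposes the gap.** A reader could set OTC aside and compare the rest. This does not cure the entry total, or the missing period that affects every type.
- **The payer perspective may shrink the OTC share.** Section 10.4 costs from the third-party payer's perspective and does not say how much OTC spending counts. If little does, s is near zero and only the period problem remains.
- **The look-back could be printed on the CRF, which is not shown.** That is possible. It would not settle whether V1 use is collected, nor supply OTC data.

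**Conclusion.** The point holds in a limited form. The protocol plans an entry cost column while contradicting itself on whether the data for it are collected. It gives that column no period, and does not collect one named cost input at V1. The entry total is therefore not on the same footing as the 6- and 12-month totals.

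The size cannot be fixed from the documents. Over the assumed ranges (W from 1 to 12 months, s from 0 to 30%), the apparent change from entry to month 6 runs from −50% to +757% with no true change. With a matching 6-month look-back it is 0% to +43%. These figures illustrate sensitivity and are not estimates.

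The consequence is confined to the entry column and to any model that uses it. The primary cost result, cost per patient over 12 months, stands. The correction should be made, but the point does not undermine the study.

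**What to change.** In Section 10.4, report mean cost for three quantities: V1 to month 6, months 6 to 12, and the 12-month total. For the entry column, choose one of two:

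1. Drop it.
2. Set a 6-month look-back on the V1 CRF, and show across visits only the items collected at all three, which excludes OTC medication.

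Reconcile Section 4 and Sections 7.6, 7.9, 7.9.1 and 8.1 on whether resource use is recorded at V1, and bring the synopsis into line with the result.

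The cost is mostly wording. Option 1 loses a baseline cost description. Option 2 limits it to common items and adds one line to the V1 CRF.

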10.5 Calculation of Indirect Costs: Productivity

Days of work missed due to GERD and obtained from the WPAI-GERD will be converted into monetary amounts utilizing earnings data from the national statistics (INSEE).

The mean cost of productivity loss will be reported by visit (at study entry, 6 months and 12 months) and type of productivity loss (absenteeism, presenteeism, overall).

The mean cost of productivity loss will also be reported by physician type (GP vs specialist), patients' characteristics (age class, gender, BMI class) and frequency and severity of symptoms.

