- The Hospital Anxiety and Depression Scale (HADS) is a 14-item self-assessment designed to detect states of anxiety and depression among patients in an outpatient clinic setting.²³ Each item is answered by the patient on a four point (0–3) response category. The HADS yields an anxiety score and a depression score.

Work Productivity

- The Work Productivity and Activity Impairment for Patients with Gastroesophageal Reflux Disease (WPAI-GERD) questionnaire is a six question instrument that measures work productivity and activity impairment instrument over the past seven days due to GERD.²⁴ It yields four types of scores; absenteeism (work time missed), presenteeism (impairment at work / reduced on-the-job effectiveness), work productivity loss (overall work impairment / absenteeism plus presenteeism) and activity impairment. WPAI outcomes are

expressed as impairment percentages, with higher numbers indicating greater impairment and less productivity.

Patient resource utilization

A patient resource utilization instrument investigating about any over the counter medication taken by the patient during the 12 months during the study, as well as visits to other physicians will be provided to the patient together with the survey at month 3, 6, 9 and 12. A memory aid will allow the patient to track their medication between the survey dates.

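### Section 10.5 puts a money value only on days of work missed, so it does not yield the presenteeism and overall costs it promises, and it reports productivity cost at three of the five WPAI-GERD assessments

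*Protocol*

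**What the plan says.** Protocol section 10.5 fixes how work loss becomes a cost: "Days of work missed due to GERD and obtained from the WPAI-GERD will be converted into monetary amounts", using earnings data from the national statistics office. The next sentence sets the outputs. Mean cost is to be reported "by visit (at study entry, 6 months and 12 months") and by "type of productivity loss (absenteeism, presenteeism, overall").

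Section 7.9.2 describes the instrument. The WPAI-GERD looks back seven days and gives four scores, each an impairment percentage. Absenteeism is work time missed and presenteeism is reduced effectiveness on the job. The third score is "work productivity loss (overall work impairment / absenteeism plus presenteeism"), and the fourth is activity impairment. Section 10.3 likewise explains presenteeism as being at work with reduced productivity, and reports the non-cost productivity results by visit without limiting the visits.

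The schedule in section 7.9 marks the WPAI-GERD at all five time points, V1 and months 3, 6, 9 and 12: "WPAI-GERD) 6 X X X X X". Section 10.4 reports direct costs at study entry, 6 and 12 months, which are the points at which the schedule places the physician-reported resource data.

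**The concern.** Two neighbouring sentences of 10.5 do not fit together. The first values a quantity that measures absenteeism only. The second promises a presenteeism cost and an overall cost, neither of which can be derived from days missed. An analyst who keeps to the first sentence cannot fill the tables that the second requires, and an analyst who fills them must use a valuation rule that the protocol does not contain.

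The time points are a second mismatch. They match the direct-cost schedule of 10.4, not the schedule of the instrument from which productivity cost is calculated.

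Work productivity and cost per patient are both primary objectives (section 3.1). The productivity costs are also to be broken down by physician type, patient characteristics and symptoms (10.5), and 10.6 plans models for productivity losses and costs. An unstated valuation rule would carry through to all of these.

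**Working it through.** The study is descriptive and the protocol states no productivity-cost figure to reproduce. The check compares the rule with the promised outputs, then the cost visits with the collection schedule.

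**1. Which promised cost follows from the rule?**

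| Cost type promised (10.5) | Quantity needed (7.9.2, 10.3) | Obtained from days missed? |
|---|---|---|
| Absenteeism | Work time missed | Yes |
| Presenteeism | Reduced output while at work | No, no day is missed |
| Overall | Both components | No, one component has no value |

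One of three follows. Section 10.4 deals with healthcare resources and 10.7 lists healthcare resource types only, so neither supplies the missing valuation.

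**2. Which assessments are costed?**

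- Collected (7.9): months 0, 3, 6, 9 and 12, so 5.
- Costed (10.5): months 0, 6 and 12, so 3.
- Not costed: months 3 and 9, so 2/5 = 40%.
- Follow-up points costed: 2 of 4.
- Days covered by the seven-day recall: 3 x 7 = 21 (21/365 = 5.8% of a year) against 5 x 7 = 35 (35/365 = 9.6%).

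**3. How large could the unvalued part be?** The protocol gives no impairment levels, so the values below are assumptions. For this illustration, A is the share of scheduled work time missed and P is the share of output lost in the time worked. Per 100 units of scheduled earnings, missed time costs 100A, impaired time costs 100(1 - A)P, and the share valued by the days-missed rule is A / [A + (1 - A)P].

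| A | P | Missed | Impaired | Combined | Share valued |
|---|---|---|---|---|---|
| 1% | 10% | 1 | 99 x 0.10 = 9.9 | 10.9 | 9.2% |
| 1% | 30% | 1 | 99 x 0.30 = 29.7 | 30.7 | 3.3% |
| 5% | 10% | 5 | 95 x 0.10 = 9.5 | 14.5 | 34.5% |
| 5% | 20% | 5 | 95 x 0.20 = 19.0 | 24.0 | 20.8% |
| 5% | 30% | 5 | 95 x 0.30 = 28.5 | 33.5 | 14.9% |
| 10% | 30% | 10 | 90 x 0.30 = 27.0 | 37.0 | 27.0% |

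For A of 1% to 5% and P of 10% to 30%, the share valued runs from about 3% to 34%. Using a plain sum A + P in the denominator gives 3.2% to 33.3% over the same range, so the illustration hardly depends on how the two components are combined.

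**The case against.** The strongest reply is that 10.5 names presenteeism as a cost type and merely leaves out its formula. The score is collected (7.9.2) and described by visit (10.3), and section 10.1 promises a formal analysis plan in which a conversion formula could stand. Common visits for direct and indirect costs are a defensible reporting choice. Months 3 and 9 are not lost either: 10.3 reports productivity loss by visit without restriction, and the longitudinal models in 10.6 cover productivity loss.

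Much of this stands, and it limits the finding. Presenteeism and overall costs are out of reach of the stated rule, not of the data, and months 3 and 9 are left out of the cost reporting, not of the study. The reply does not remove the finding, because the protocol is not silent. It fixes a days-missed rule and then promises outputs that the rule does not give. An analysis plan could resolve this only by going beyond the protocol's text.

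Four stronger readings are tempting, and the protocol supports none of them.

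- A reader might infer that the reported cost will be too low by the whole presenteeism component. Nothing tells the analyst to enter zero for presenteeism or to equate overall with absenteeism.
- A reader might infer that the entry week, in which criterion 5 requires symptoms, gets too much weight in an annual figure. Section 10.5 reports by visit and defines no annual indirect total, so there are no weights to criticise.
- A reader might infer a definite loss of precision from using three visits. Any such figure would depend on an annual estimator that the protocol does not specify.
- A reader might infer double counting from the description of overall loss in 7.9.2. That is a short gloss on an instrument score, not an analysis formula, and the protocol does not state the bases of the percentages.

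**Conclusion.** The point holds in a limited form. As written, the valuation rule in 10.5 delivers absenteeism cost only, one of the three promised outputs, and the section leaves two of the five scheduled WPAI-GERD assessments out of the reported productivity costs. Both statements rest on the protocol's text alone.

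The size in money is unknown, because the protocol gives neither wages nor impairment levels. The range of about 3% to 34% shows what a literal days-missed calculation would value under assumed inputs. It does not predict what the study will report.

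The gap is small to close but bears on primary objectives, so 10.5 should be corrected before the cost analysis is programmed.

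**What to change.** Reword 10.5 as follows.

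- Value both work time missed and impaired time at work (time worked x presenteeism percentage) at INSEE earnings.
- Report absenteeism cost and presenteeism cost separately, and overall cost as the two combined.
- Report these costs at all five WPAI-GERD assessments: V1 and months 3, 6, 9 and 12. The entry, 6 and 12 month results can still be set beside the direct costs.
- If a 12-month indirect cost per patient is calculated, base it on all five assessments and state how the seven-day windows are scaled to the year.

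The cost is a few sentences in one section. No extra visit or questionnaire is needed, since the WPAI-GERD is already scheduled five times. The protocol does not reproduce its items, so the sponsor should confirm that time worked is recorded. The one downside is that presenteeism cost depends on self-rated impairment, which is the reason to show the two components apart.

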10.6 Multiple regression

To investigate the link between symptom (frequency and severity) and QOL we propose to conduct a number of analyses consisting of correlation analysis, graphical analysis and generalised linear modeling. GLM are selected to account for underlying distribution of endpoint of interest (non-normal). We would model QOL score as a function of patients' characteristics, symptoms, adverse effects and medical history, to quantify the impact of each factor on the QOL impairment. Similar types of analyses would be performed for resource use, productivity losses and costs.

In addition we will develop longitudinal models to understand the evolution of the study endpoints over time to quantify the consequences of reducing the symptom frequency and/or severity in terms of costs, quality of life and utility values. We would use generalized estimating equation modeling to model the study endpoint dynamically and account for the between-patient heterogeneity. Generalised Estimating Equation models would be used here to estimate the heterogeneity between-patients vs within patient and to understand the impact of change in symptoms (reduction of frequency, severity) on study endpoints. These analyses would be performed for HRQOL, utility values, productivity loss, healthcare resource use.

Bivariate analyses will be conducted to assess whether each factor of interest (patients' characteristics and symptoms frequency and severity) significantly affects quality of life, resource use, productivity loss and associated costs. The heterogeneity between sites and between patients will be reported via the analysis of intraclass coefficients.

The results of these preliminary analyses will be used to develop generalized linear mixed model, accounting for the underlying distribution of the modeled endpoints and the clustering of the data (patient's repeated measures nested within sites).

10.7 Cost of Illness Analysis

The first step of this analysis will consist of estimating the size of the target population. A literature review will be undertaken to obtain the incidence and prevalence of GERD in France and the proportion of patients treated in primary care and secondary care. The proportion of

patients with GERD with incomplete response to PPI will be calculated from the sites' log. The proportion of partial responders will be reported by site, physician type and overall, together with 95% confidence intervals. The size of the target population (partial responders to PPI) in France will then be derived.

Based on the information obtained from the cost of healthcare resources collected alongside this study, we will be able to estimate the cost of partial response to PPI within the year of partial response diagnosis. Some assumptions will be made on the basis of the literature and clinical experts' opinion to estimate the mean cost of treatment over subsequent years. The cost of partial response to PPI will be reported overall and by type of resource (GP visits, specialist visits, diagnostic tests, hospitalization, prescribed medications and OTC medications) for France.

